Those who choose to participate in self-testing will be asked to keep the used kit in an opaque bag and give the anonymized self-test kit to the study team during the brief exit survey. The study team will NOT look at the test results, but will staple the opaque bag closed, link the unique identification number on the test bag to the exit survey, and drop the self-test kit into a secure lockbox. Those who do not want to directly give the self-test kit to the study team will be allowed to dispose their test kit in a lockbox located in the waiting area or a lockbox located in the provider consultation room.

After completing the OPD or STI consultation, clients aged 15 years and older will be asked to participate in a brief 15 minute, anonymized exit survey about their experience with self-testing why they chose to use the kit or not. We will recruit all eligible OPD and STI clients for the survey – including clients who used self-testing and those who opted-out of self-testing. Survey participation is completely voluntary and can be refused at any point. Those who self-report as testing HIV positive with a self-test kit will complete written consent and will provide identifiable information so the study can prospectively track linkage to care.

HIV testing registers, ART registers, OPD registers, and STI registers will be reviewed to triangulate the (1) number of individuals attending OPD and STI clinics over the study period (denominator), (2) number of OPD and STI clients tested for HIV (numerator), (3) proportion of those tested who are identified as HIV-positive (defined as a positive HIV test from two different types of tests – Determine and Uni-Gold), and (4) proportion of those identified as HIV-positive who linked to ART services. All data will be anonymized from existing registers. Records from OPD and STI clients aged 15 years and older will be included in the study. Over the study period, we will be able to determine the proportion of all STI and OPD patients who receive an HIV test, the proportion of those tested who are HIV-positive, and the proportion of HIV-positive clients who link to ART services. We will also be able to determine differences by age sex, and service type.

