2.4.2. Optimized Standard of Care Arm

2.4.2.1 *Provider Initiated Testing and Counseling (PITC)*

Facilities randomized to the optimized standard of care arm will provide standard PITC as recommended by the Ministry of Health. Facilities will be supported by the study team with initial trainings on the importance of HIV testing, the role of HIV testing as part of outpatient and STI care, and strategies used to discuss HIV testing with patients. The study team will also provide job aids to remind providers about the importance of referring patients for HIV testing and assist in the monitoring and evaluation of PITC implementation. When clients are referred for testing, they will use the standard HIV testing services room located in the same health facility. Testing will be available during all clinic hours and completed by trained HIV Diagnostic Assistants (HDA) who work at the facility (i.e., non-study staff). HIV testing for OPD and STI clients will follow Ministry of Health National Guidelines using HDAs who will provide individual counseling and serial testing with Determine and Uni-Gold HIV test kits. Discordant results will result in re-testing using the MOH guidelines. Those with positive HIV tests will be counseled and referred to ART services following routine care.

2.4.2.2. *Demographic Data Collection*

Clients in the optimized standard of care arm who complete an OPD/STI consultation visit will meet briefly with a study staff member after their visit. The study staff member will collect anonymous demographic data including age, gender, highest level of education, and reason for visit to OPD/STI clinic. It will also capture if clients were offered testing, if they were tested, self-reported test result, and why they chose to test or not.

2.4.2.3 *Additional Data Collection for those who: (1) test HIV positive that same day; (2) have not tested but want to test for HIV that same day, Participants who self-report as having (1) tested HIV positive that same day or (2) not tested but want to test for HIV that same day* will be asked to complete written consent for collection of identifiable information in order to track linkage and retention to ART.

2.4.2.3. *Registry Data for Triangulation and Linkage*

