2.4.3. Group Self-Testing Arm

A trained study member will meet with clients waiting in the OPD and STI waiting spaces and read the oral consent script explaining that participation in self-testing and study procedures is voluntary. The HDA will then provide group education in the OPD and STI waiting areas about (1) the benefits of HIV testing and treatment, (2) a demonstration of how to use a self-test kit and who should use the kit for testing, and (3) and group counseling about follow-up needed for both HIV negative (re-testing at regular intervals) and positive results (referral for confirmatory testing and ART initiation and follow-up). All individuals 15 years of age and older in the waiting area will be offered a self-test kit.

Clients who tested HIV negative within the past 3 months, previously tested HIV positive, are currently taking ART, are uncomfortable administering the self-test kit, or would like to receive an assisted HIV test either through standard HIV testing protocols or a provider observed HIV self-test kit will be advised to opt-out from the HIV self-test. Those who would like to opt-out for any reason will be asked to take a kit and give the unopened kit to the research team during a brief exit survey.

Those who would like to take the self-test will perform the test while waiting for their appointment. In order to avoid unintended disclosure to participants sitting in the waiting area, after the sample is obtained, individuals will be instructed to put the kit into the opaque testing bag while waiting for the test results in order to ensure privacy and minimize risk of adverse outcomes due to unintended disclosure (approximately 20 minutes). Participants will be allowed to perform the self-test while seated in the waiting area or may move to a more private location on the facility grounds. A private space (tent or other sectioned off area of the waiting area) will be available for individuals who wish to read their test before entering the provider consultation room. After completing the test, participants may do any of the following:

- Individuals who are willing to share the result with the provider will be asked to bring their kit to the provider for interpretation and counseling.

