- Individuals will be asked to give the anonymized self-test kit to the study team during the brief exit survey. The study team will NOT look at the test results, but will staple the opaque bag closed, link the unique identification number on the test bag to the exit survey, and drop the self-test kit into a secure lockbox. Those who do not want to directly give the self-test kit to the study team will be allowed to dispose their test kit in a lockbox located in the waiting area or a lockbox located in the provider consultation room.

Trained research assistants and an HDA will be available in the waiting area to answer any questions.

2. *Test Interpretation and Confirmatory Testing*

Participants who test positive with the self-test method and disclose results to the provider will be referred to an HDA to have confirmation testing conducted with routine Ministry of Health testing guidelines. These individuals will receive standard of care counseling by facility HDAs and be referred for ART initiation if their confirmatory HIV test is positive.

2.4.3.4. *Demographic Data Collection*

Participants in the group self-test arm who complete an OPD/STI consultation visit will meet briefly with a study staff member after their visit. The study staff member will collect anonymous demographic data including age, gender, highest level of education, and reason for visit to

OPD/STI clinic. They will also ask whether or not participants performed the HIV self-test, what motivated them to use/not use the self-test, and self-reported test result (if willing to disclose). For those willing, the study staff member will also collect the self-test kit, staple the opaque bag closed (if used), link the unique identification number on the test bag to the exit survey, and drop the self-test kit into a secure lockbox. The study staff member will NOT look at test results.

2.4.3.4 Additional Data Collection for those who: (1) test HIV positive that same day; (2) have not tested but want to test for HIV that same day

Participants who self-report as having (1) tested HIV positive that same day or (2) not tested but want to test for HIV that same day will be asked to complete written consent for collection of identifiable information in order to track linkage other HIV services.

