2.4.4.1. Registry Data for Triangulation and Linkage

HIV testing, ART, OPD, and STI registers will be reviewed to measure the number of individuals attending the clinics during the period of the study (denominator), the number HIV tested using routine testing strategies (numerator), the proportion of those tested through routine test strategies who are identified as HIV-positive (yield), and the proportion of those identified as HIV positive who link to ART services. All data will be anonymized from existing registers. Records from OPD and STI clients aged 15 years and older will be included in the study. Over the period of the study, we will be able to determine the proportion of all STI and OPD patients who received a routine HIV test (Determine and Uni-Gold HIV test kits), the proportion of those tested who are HIV-positive, and the proportion of HIV positive clients who linked to ART services.

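### The Aim 1 exit survey asks about any HIV test in the two comparator arms but only about self-test use in the self-testing arm, and section 2.5.1 names no source for the primary numerator

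*Combined protocol and SAP*

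**What the plan says.** For the optimized arm, section 2.4.2.2 describes the exit survey thus: "It will also capture if clients were offered testing, if they were tested, self-reported test result, and why they chose to test or not". Section 2.4.1.2 repeats this under the standard of care heading, although its text names the optimized arm. Section 2.3.2 gives the same any-test content for both arms.

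For the self-testing arm, the demographic data paragraph in section 2.4.3 reads "They will also ask whether or not participants performed the HIV self-test", followed by the reasons for using or declining the kit and the self-reported result. Section 2.3.2 agrees, describing an "anonymized exit survey about their experience with self-testing why they chose to use the kit or not". Neither description lists an item on a test done by another route.

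Section 2.4.3 also says that clients who "would like to receive an assisted HIV test either through standard HIV testing protocols or a provider observed HIV self-test kit will be advised to" opt out. They are asked to hand back the kit unopened at the exit survey.

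Registers are reviewed in this arm too. Section 2.4.4.1 lists "the number HIV tested using routine testing strategies (numerator", and identifies routine tests as Determine and Uni-Gold. The register data are anonymised. Section 2.4 states that data collection is the same in every arm. Section 2.5.1 defines the outcome as the proportion of participants tested, with no data source.

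**The concern.** The primary comparison is the proportion tested under group self-testing against optimized care. As described, the survey measures any test in two arms and self-test use in the third. The protocol itself creates the group on which these definitions differ: clients advised to leave the self-test because they prefer an assisted test, some of whom may be tested that day.

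Cost-effectiveness is also a primary objective (section 2.1.1). Section 2.6 averages cost over individuals who complete a test, and section 2.6.1 costs Determine and Uni-Gold kits. An HDA test in the self-testing arm could therefore add cost while the person tested is missing from the denominator. Any loss would fall on clients who cannot or will not use the kit themselves, so comparisons by age or sex could also be affected.

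**Working it through.** **1. What each source captures in the self-testing arm**

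| Route | Exit survey (2.3.2, 2.4.3) | Register (2.4.4.1) |
|---|---|---|
| Unassisted self-test | Yes | No |
| HDA test after opting out | No item listed | Yes, but anonymised |
| Provider-observed self-test | Unclear: the client has opted out and may answer no | Not clearly: the count is of routine tests |
| HDA confirmation of a positive self-test | Already counted as a self-test | May appear again |

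Section 2.3.3 limits identifiers to same-day positives and to untested clients who want a test that day. A register entry therefore cannot generally be matched to a survey participant. The register denominator is all attendees, whereas section 2.5.1 plans on 1,000 participants per cluster.

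**2. The plan's power figure.** Inputs from section 2.5.1: 5 clusters of 1,000 per arm, intra-cluster correlation 0.004, type I error 0.05, coverage 5%, at least 10%, and 60%.
- Design effect: 1 + (1,000 − 1) × 0.004 = 4.996. Effective sample per arm: 5,000 / 4.996 = 1,001.
- 5% against 10%: power 98.9% (two-sided normal) or 96.0% (cluster-level t, 8 degrees of freedom).
- 10% against 60%: about 100%.

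The stated figure of at least 95% is reproduced.

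**3. Survey as sole numerator.** The plan gives no assisted-test share for this arm. Read 60% as self-test uptake, so that 40% do not self-test, and borrow the plan's comparator coverage as the assumed share of these who get an HDA test:
- 0.40 × 0.05 = 0.02
- 0.40 × 0.10 = 0.04

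Any-test coverage would be 62–64% and the survey would show 60%.

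**4. Survey plus register.** Assume 60% self-test, 2–10% of these are positive, and 50–100% of positives have HDA confirmation entered in the register. None of these positivity or confirmation figures is in the documents.
- Low: 0.60 × 0.02 × 0.50 = 0.006
- High: 0.60 × 0.10 × 1.00 = 0.06

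A simple sum would count 0.6–6 points twice, the opposite direction from step 3.

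**5. Cost, under step 3 with costs fixed.**
- Cost per person tested is too high by 62/60 = 1.033 to 64/60 = 1.067, or about 3–7%.
- The difference from 10% is recorded as 50 points instead of 52–54, so cost per additional person tested is too high by 52/50 = 1.04 to 54/50 = 1.08, or 4–8%.

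**6. Power under an undercount.** Read 60% instead as true any-test coverage and let the survey miss x points. At x = 1, 5, 10 and 20 the recorded coverage is 59%, 55%, 50% and 40%; the difference from 10% is 49, 45, 40 and 30 points; power stays about 100%. It falls below 95% only when recorded coverage drops under about 15.4% (normal) or 16.3% (t), a loss of about 44 points.

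**The case against.** The strongest reply is that the plan does count HDA tests in this arm. Section 2.4.4.1 provides for routine tests, and the register passages are where the word numerator appears. A reader might infer that opted-out clients are counted as untested in the primary outcome. No section says so; it follows only if the survey alone supplies the numerator. Nor do the documents support a flat statement that coverage is understated, since adding register counts could overstate it. Both points stand. They move the problem to section 2.5.1, which neither chooses a source nor gives a rule for combining two largely unlinkable ones.

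The questionnaire is not in the documents, so the survey content is known only from prose summaries. The survey must also pick out clients positive that day and clients not tested but wanting a test (sections 2.3.3 and 2.4.3), which implies some wider question about testing. That would not identify a client who opted out and had already tested negative with an HDA. Some observed self-tests may be reported as self-tests performed.

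The size is also open to challenge. Section 2.5.1 calls 60% testing coverage. If that means any test, the other 40% are untested by definition and step 3 does not apply. The 40% would also include known positives, clients on ART and recent negatives, who are unlikely to seek a test that day. A reader might infer a larger loss: an assisted-test share of 20% would give 0.40 × 0.20 = 8 points, but that is twice the 10% the plan uses for optimized care and has no source.

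**Conclusion.** The difference in survey content is in the text and conflicts with the statement in section 2.4 that all arms are measured alike. Neither source alone gives an any-test outcome in the self-testing arm that matches the comparator surveys. Whether this undercounts or double-counts depends on a choice that section 2.5.1 leaves open.

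The size cannot be fixed from the documents. The 2–4 points rest on two assumptions: that 60% is self-test uptake, and that comparator-arm coverage carries over to clients who do not self-test. Against a planned difference of 50 points this does not threaten the superiority test, and an undercount would work against self-testing. A reader who infers a loss of power would be mistaken. The consequence is for the coverage estimate, the cost per person tested and the cost-effectiveness ratio. The change should be made, but the trial's main conclusion does not hang on it.

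**What to change.** Use one survey item in all three arms: *Were you tested for HIV here today, and how: self-test, observed self-test, HDA test, none?* List it in sections 2.3.2, 2.4.1.2, 2.4.2.2 and 2.4.3, so that the statement in section 2.4 becomes true.

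State in section 2.5.1 that the primary numerator is survey participants who report any test, each counted once; that self-test uptake is reported as a component; and that registers serve only for triangulation. Use the same numerator in sections 2.6 and 2.6.2.

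The cost is one survey item and a few lines of text. Two limits remain: the outcome rests on self-report, and HDA tests done after the exit survey would still be missed.

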2.4.4. Post-Intervention Interview

A random subset of 60 OPD/STI clients (30 men and 30 women) in the group self-test arm will be asked to participate in an in-depth qualitative interview. These individuals will be selected from at least three different facilities in the group self-test arm and stratified by sex, use of self-testing (or not), and among those self-reporting a positive self-test result, HIV status. In the interview, participants will be asked about their experience with group self-testing, including concerns about privacy, problems performing or interpreting the test, and any perceived harms or benefits resulting from group self-testing.

2.4.4.1. Registry Data for Triangulation and Linkage

HIV testing, ART, OPD, and STI registers will be reviewed to measure the number of individuals attending the clinics during the period of the study (denominator), the number HIV tested using routine testing strategies (numerator), the proportion of those tested through routine test strategies who are identified as HIV-positive (yield), and the proportion of those identified as HIV positive who link to ART services. All data will be anonymized from existing registers. Records from OPD and STI clients aged 15 years and older will be included in the study. Over the period of the study, we will be able to determine the proportion of all STI and OPD patients who received a routine HIV test (Determine and Uni-Gold HIV test kits), the proportion of those tested who are HIV-positive, and the proportion of HIV positive clients who linked to ART services.

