HIV testing, ART, OPD, and STI registers will be reviewed to measure the number of individuals attending the clinics during the period of the study (denominator), the number HIV tested (numerator), the proportion of those tested who are identified as HIV-positive (yield), and the proportion of those identified as HIV positive who link to ART services. All data will be anonymized from existing registers. Records from OPD and STI clients aged 15 years and older will be included in the study. Over the period of the study, we will be able to determine the proportion of all STI and OPD patients who receive an HIV test, the proportion of those tested who are HIV-positive, and the proportion of HIV positive clients who linked to ART services.

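### Aim 1: register yield in the self-testing arm is defined on routine tests only, so positivity is inflated and not comparable with the other arms

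*Combined protocol and SAP*

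**What the plan says.** Section 2.4.4.1 describes the register data for the self-testing arm. The coverage numerator is "the number HIV tested using routine testing strategies (numerator" and yield is "the proportion of those tested through routine test strategies who are identified as HIV-positive (yield". The section then speaks of clients who "received a routine HIV test (Determine and Uni-Gold HIV test kits", so the self-test kit is not a routine test.

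The register paragraph for the optimized arm, in section 2.4.2, has no such limit. Its numerator is "the number HIV tested (numerator" and its yield is "the proportion of those tested who are identified as HIV-positive (yield". Section 2.3.2 describes the self-testing arm's register numerator a second time, as "number of OPD and STI clients tested for HIV (numerator", again without the limit. It also defines HIV-positive as positive on two different tests, Determine and Uni-Gold.

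Under section 2.4.3, a client with a positive self-test who tells the provider "will be referred to an HDA to have confirmation testing conducted with routine Ministry of Health testing guidelines". On self-test use, the same section says of the exit survey staff: "They will also ask whether or not participants performed the HIV self-test". Returned kits are linked to the survey by ID. The result is recorded only if the client is willing to report it, and study staff do not read the kits.

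Section 2.5.1 names two outcomes for comparison by arm, the proportion tested and positivity in those tested. It plans coverage of 5%, 10% and 60% in the three arms. It does not say which source supplies either outcome.

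**The concern.** One label, yield, covers two denominators. In the optimized arm it is everyone tested. In the self-testing arm it is the people who had an HDA test, and some of those were sent there because a self-test was already reactive. Clients whose self-test was negative, who should make up most of the denominator, never enter it.

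Higher yield is a stated hypothesis for Aim 1, and positivity in those tested is an outcome compared by arm. If section 2.4.4.1 is followed, self-testing would show a higher yield than provider-initiated testing even if the people tested in the two arms were equally likely to be positive. Sections 2.6 and 2.6.2 also rely on cost per person tested and cost per positive identified, and cost-effectiveness is a primary objective. Those figures need a count of people tested by either method, each counted once.

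**Working it through.** **The plan's own figure.** With 1,000 clients per cluster, 5 clusters per arm and ICC 0.004, the design effect is 1 + 999 × 0.004 = 4.996 and the effective size is 5,000/4.996 = 1,001 per arm. Two-sided power at 0.05 is above 0.999 for 10% against 60%, and 0.989 for 5% against 10%. The stated power of at least 95% reproduces, and this point does not change it. The 60% is plausible only if self-tests count as tests.

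**Inputs per 1,000 clients in the self-testing arm**
- Self-testers: 600 (section 2.5.1).
- Assumed: positivity 5% in everyone tested; self-test results correct; 50% of reactive clients disclose and are confirmed; 50 opt-outs have an HDA test.
- Comparator: 100 tested per 1,000 in the optimized arm (section 2.5.1), with the same assumed 5%.

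**Register yield under section 2.4.4.1**
- Reactive self-tests: 600 × 0.05 = 30. Disclosed and confirmed: 30 × 0.5 = 15.
- Positives among opt-outs: 50 × 0.05 = 2.5.
- Routine tests: 15 + 50 = 65. Positives: 15 + 2.5 = 17.5.
- Yield: 17.5/65 = 26.9%, against 5/100 = 5% in the optimized arm.

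**Varying disclosure**

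| Disclosure | Register yield | Confirmatory share of routine tests | Confirmed positives over all 650 tested |
|---|---|---|---|
| 25% | 10/57.5 = 17.4% | 7.5/57.5 = 13% | 10/650 = 1.5% |
| 50% | 17.5/65 = 26.9% | 15/65 = 23% | 17.5/650 = 2.7% |
| 100% | 32.5/80 = 40.6% | 30/80 = 37.5% | 32.5/650 = 5.0% |

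**Direction.** With S self-testers, R routine tests in opt-outs, positivity p and disclosure d, register yield divided by p is (S·d + R)/(S·p·d + R). This exceeds 1 whenever d > 0 and p < 1. In the base case it is 350/65 = 5.4.

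**Wider range.** Take p from 2% to 10%, d from 25% to 100%, and routine testing in 5% to 10% of the 400 who do not self-test (20 to 40 tests), all assumed. Register yield then runs from 3.8/43 = 8.8% (at p = 2%) to 62/80 = 77.5% (at p = 10%). The smallest inflation is 19/55 = 34.5% against 10%, or 3.45-fold. Confirmatory tests are 3/43 = 7% to 60/80 = 75% of routine tests.

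**Coverage in the base case.** The register alone gives 65/1,000 = 6.5%. Any method gives 650/1,000 = 65%.

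**Per attendee in the base case.** Confirmed positives are 17.5/1,000 = 1.75% in the self-testing arm and 5/1,000 = 0.5% in the optimized arm.

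**The case against.** The strongest reply is that section 2.4.4.1 is headed as triangulation and linkage data. It describes what existing registers contribute and does not define the trial outcome. Much of this stands, and it rules out three stronger readings.

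- **Self-tests are lost from coverage.** A reader might infer this from the routine-only numerator. The documents do not support it. The exit survey asks about self-test use, kits are linked to it by ID, section 2.3.2 states the numerator without the limit, and the planned 60% presupposes that self-tests count. The 6.5% would apply only if the register were the sole source, and no section says so.
- **Yield rests largely on confirmatory tests.** In the base case they are 15 of 65. Over the wider range their share runs from 7% to 75%, so a majority is possible but not assured. The inflation does not need one.
- **The survey misses opt-outs tested by an HDA, and positives will be counted twice.** The item listed for this arm concerns the self-test, whereas the other arms' surveys ask whether the client was tested. But the questionnaire is not in the documents, and section 2.4 says data collection is the same in all arms. No section proposes adding register counts to self-test counts. Clients who self-report a positive result are asked for identifiers, so those who consent could be matched.

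It is also true that section 2.1.2 frames yield as how many HIV-positive people are found, which registers can supply per attendee in every arm.

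Triangulation does not rescue positivity in those tested. Being HIV-positive requires two routine tests, so confirmed positives can come only from HDA testing, and the only yield denominator that section 2.4.4.1 sets for that source excludes self-testers.

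**Conclusion.** The point holds for positivity in those tested. Section 2.4.4.1 states a rule that gives a biased between-arm comparison. The direction follows from the definition whenever some reactive clients disclose. The size depends on rates the documents do not give: 27% against 5% in the illustration, and at least 3.45-fold over the assumed range.

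For coverage the fault is narrower. Sections 2.3.2 and 2.4.4.1 define the same register numerator differently, and section 2.5.1 names neither a source nor a rule for combining register, survey and kits. The primary coverage comparison is not shown to fail.

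A common denominator does not by itself make the arms comparable. At equal 5% positivity, confirmed positives over all tested reads 2.7% in the self-testing arm at 50% disclosure, because undisclosed positives stay in the denominator. The correction therefore needs a per-attendee measure and a sensitivity analysis as well.

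**What to change.** Reconcile sections 2.3.2, 2.4.2, 2.4.4.1 and 2.5.1 as follows.

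1. In the self-testing arm, define tested as having completed a self-test (from survey or kit) or having had an HDA test that day, with each client counted once. Name the source for each part in section 2.5.1.
2. In every arm, define positivity as two-test-confirmed positives divided by persons tested by any method.
3. In every arm, also report confirmed positives per clinic attendee, which matches the yield objective in section 2.1.2.
4. Make sure the self-testing exit survey records whether the client was tested by an HDA that day.
5. Have HDAs mark register entries that are confirmatory after a self-test, so that they are not counted as additional tests.
6. Report self-reported reactive but unconfirmed results separately, with a sensitivity analysis over a range of disclosure rates.

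The cost is an agreed definition, one survey item and one register mark. The survey item and the mark have to be in place before data collection, because anonymous records are hard to de-duplicate afterwards. The downside is that the reported self-testing yield becomes much less favourable than the register-only figure.
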